**8) Procedures Involved\***

Any member of the study team will discuss potential subjects with the clinical team for appropriate pursuit of informed consent and screening for eligibility.

75 eligible subjects, after consent, will have laboratory blood tests for further screening.

25 of those subjects with endogenous **AT3  $\geq$  100%** will continue with SOC.

50 of those subjects with endogenous **AT3 < 100%** will be will be randomly assigned to begin **SOC plus treatment with exogenous AT3 supplementation or only SOC** treatment. The randomization schedule will be established by a member of the study team that is not involved in the informed consent process.

They will all be followed up for laboratory blood tests, study endpoints and adverse events. If they do not meet entry criteria they will be excluded from the study.

[figure not shown]
Consented subjects will be scored according to The International Society of Thrombosis and Haemostasis Disseminated Intravascular Coagulation scale (ISTH DIC) on study visit days 1, 3, 5, 7, 9 and 11.

The SOFA score will be performed only when the parameter is obtained clinically and monitored for changes in patient status on study visit days 1, 3, 5, 7, 9 and 11. Each organ system is assigned a point value from 0 (normal) to 4 (high degree of dysfunction/failure). It will be calculated on admission and Day 11 using the worst parameters measured during the study visit day. If a parameter is not obtained clinically it will be voided for research purposes.

UM IRB# 20201048

AT3 in COVID-19  
January 24, 2022, Version 6.2

After enrollment and each 48h period (+/- 12 hours) thereafter, blood samples are collected and assayed for routine clinical coagulation and inflammation markers, including AT3 activity, D-Dimer, anti-Xa, fibrinogen, and prothrombin time until Day 11.

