### Dosing Rationale-

In those COVID(+) patients with an endogenous AT3 activity level <100% and at the discretion of the attending physician, Day 1 infusion of AT3 will be at a dose to be adjusted based on initial body weight up to 100 kg maximum and to a set target plasma activity level of 120% according to the following formula:

$$= \frac{(120\% - \text{baseline AT3}\%)}{1.4} \times \text{body weight (kg)}$$

Based on an example of an 85kg patient with a baseline AT activity level of 90%,

- The dose would be 1,821 units on a dosing schedule of Day 1, 3, 5, 7 & 9
- For a total of approximately 9100 units
- Each Thrombate III vial contains 500 units each reconstituted with 10 mL of Sterile Water for Injection, USP, the final concentration is approximately 50 units per mL.
- Requiring 4 vials per dose or 20 vials per patient

Each 85kg patient will receive ~9100 IU's over 5 doses requiring 20 vials

- (10% overage to account for any dose adjustments needed)
- therefore each patient would require 10,000 IU's
- for a total of 250,000 IU's or 500 vials for the study.

AT3 will be drawn every other day, pre-dose, for monitoring, and verification of 120% target plasma activity level. Dosing schedule will be as follows: Day 1, 3, 5, 7 & 9 a dose will be given if AT3 activity level remains less than 100% on those days, otherwise no dose will be given. Days refer to a 24 hour period.

Data to be collected from the medical record according to the Study Flowsheet (Appendix B) will include:

- a. Demographics: age, comorbidities, medical history, concomitant meds, vital signs, height and weight,
- b. ISTH DIC score and a Sofa Score,
- c. Laboratory values:
  - a. Platelets, PT, INR, PTT, D-Dimer, Fibrinogen, AT3 level, Anti-Xa,
- d. Outcomes:
  - a. Length of Stay, Mortality, change in PF ratio, Vent/ECMO days, # and severity VTE's, # and severity of bleeding events

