**Appendix B**

Study Subject Flowsheet	Enrollment - Day 1*	Days 3, 5, 7 & 9	Day 11	On Discharge
Informed Consent	x			
Entry Criteria	x			
Demographics	x			
Medical and Surgical History	x			
Prior & Concomitant Medications	x	x	x	x
Vital Sign Measurements	x	x	x	
ISTH DIC Score	x	x	x	
SOFA Score	x		x	
Blood Draw	x	x	x	
Urine or Serum Pregnancy Test if applicable	x			
Platelet	x	x	x	
PT, INR	x	x	x	
PTT	x	x	x	
Hemoglobin and Hematocrit	x	x	x	
Fibrinogen	x	x	x	
D-Dimer	x	x	x	
AT3 Level	x	x	x	
Anti-Xa	x	x	x	
Dosing if randomized to group with AT3 Infusion 	x 	x 		
Adverse Events 	x	x	x	x 
Hospital LOS				x
Mortality				x
PF ratio change				x
Days on Ventilator				x
Days on ECMO				x
VTE's				x
Bleeding Events				x

\*: Day refers to a 24 hour period.

x: To be completed

1: Only if randomized to AT3 Infusion and AT3 level is at specified level

2: Only Serious Adverse Events will be captured from last dose to hospital discharge.

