### Appendix C

The Secondary endpoint measurements:

- a. D-dimer level change from baseline to Day 9 in mcg/mL FEU or DDU,
- b. Fibrinogen level change from baseline to Day 9 in mg/dL
- c. Prothrombin time change from baseline to Day 9 in seconds
- d. Length of hospital stay in days,
- e. Mortality (%) of overall and between groups,
- f. Pulmonary function
  - a. Time (days) to mechanical ventilation and/or
  - b. ECMO Duration (days) or extracorporeal membrane oxygenation (ECMO) use,
- g. SOFA score change from baseline to Day 9 and
- h. SOFA Respiratory sub-score change from baseline to Day 9,
- i. Number of venous thromboembolisms from admission to hospital discharge,
- j. Number of major bleeding events from admission to hospital discharge

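### Section 8 voids unmeasured SOFA items without saying how they enter the total, and the plan does not fix one baseline or one follow-up day for SOFA change

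*Combined protocol and SAP*

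**What the plan says.** Section 8 takes SOFA from routine care: "The SOFA score will be performed only when the parameter is obtained clinically and monitored for changes in patient status on study visit days". The visits it lists fall on every second day from Day 1 to Day 11. On timing it adds: "It will be calculated on admission and Day 11 using the worst parameters measured during the study visit day". On gaps it says: "If a parameter is not obtained clinically it will be voided for research purposes".

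Appendix A lists six organ items, each scored 0 to 4. Appendices A and D offer an SpO2-based substitute when blood gases are missing and a modified GCS for intubated patients. The laboratory values to be collected under Section 8 are "Platelets, PT, INR, PTT, D-Dimer, Fibrinogen, AT3 level, Anti-Xa". The Appendix B flowsheet adds haemoglobin and haematocrit. Neither place includes bilirubin or creatinine, and GCS has no flowsheet row.

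Section 9 states that missing continuous values are imputed, without naming a method or mentioning SOFA.

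For timing, Appendix B places SOFA in the enrolment/Day 1 column and the Day 11 column only, and notes "Day refers to a 24 hour period". Appendix C defines the endpoint as "SOFA score change from baseline to Day 9". Section 24 has the necessary baseline data collected before the first infusion, which Section 8 places on Day 1.

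**The concern.** A change score is interpretable only if the same quantity is measured at both ends. When an item depends on a ward order, the total can be built from six items on one day and four or five on another. The difference then partly reflects which tests were ordered.

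Baseline has a related weakness. Subjects are recruited as inpatients (Section 5), so admission and study Day 1 may be different days. Taking the worst value over a 24-hour Day 1, with no pre-dose limit, can also bring values recorded after the first infusion into the baseline of the AT3 arm. An early deterioration on drug would then raise the starting point and later read as recovery.

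SOFA change and its respiratory sub-score are secondary endpoints in Section 7. Section 9 also names SOFA change as a primary outcome and uses it to divide patients into faster and slower recoverers, where a shift of 1 or 2 points can move a patient across the divide.

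**Working it through.** The plan gives no expected SOFA value, standard deviation or power figure, so there is nothing to reproduce. The check has four steps.

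**1. Which items are exposed.**
- Platelets and vital signs are scheduled on Days 1, 3, 5, 7, 9 and 11 (Appendix B). I assume vital signs include blood pressure.
- The respiratory item has the SpO2 substitute, and GCS has a modified form for intubated patients.
- That leaves the hepatic and renal items, and GCS in non-intubated patients.

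**2. Effect on an unchanged patient.** Assumed item scores (not from the plan), identical at baseline and follow-up: respiratory 3, platelets 1, hepatic 1, cardiovascular 1, neurologic 1, renal 2. Total = 3 + 1 + 1 + 1 + 1 + 2 = 9, so the true change is 0. Suppose items are voided at follow-up only:

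| Voided | Dropped from the sum | Prorated to six items | Whole score void |
|---|---|---|---|
| Hepatic | 8 − 9 = −1 | 8 × 6/5 − 9 = +0.6 | missing |
| Renal | 7 − 9 = −2 | 7 × 6/5 − 9 = −0.6 | missing |
| Both | 6 − 9 = −3 | 6 × 6/4 − 9 = 0.0 | missing |

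Voiding at baseline instead reverses the signs in the first column. The limit under dropping is 4 points per item, or 2 × 4 = 8 for hepatic and renal together. The three readings give three different results, and the plan does not choose between them.

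**3. Effect on the arm comparison, if voided items are dropped.** With follow-up void rates q1 and q0 and the same mean item score m in both arms, the spurious difference is −(q1 − q0) × m. All values are assumed:
- 30% v 10%: m = 1 gives −0.2; m = 2 gives −0.4.
- 50% v 10%: m = 1 gives −0.4; m = 2 gives −0.8.
- 30% v 30%: 0 for either m.

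**4. Baseline and follow-up day, side by side.**
- Baseline: Section 8 says admission; Appendix B says enrolment/Day 1; Section 24 puts baseline collection before dosing. Section 8 applies the worst value of the visit day and states a pre-dose limit only for the AT3 draw.
- Follow-up: Appendix C says Day 9. Section 8 monitors on Day 9 but calculates on Day 11. The flowsheet has no SOFA on Day 9.
- Possible size of post-infusion contamination: Section 13 reports reactions in 17 of 389 infusions, 17/389 = 4.4%. Over 25 first infusions that is about 1.1 patients. At 1 point each (MAP below 70 in Appendix A) the arm's mean baseline moves by 0.044 × 1 = 0.04. At the 4-point maximum it moves by about 0.17. Those subjects had congenital deficiency, so applying the rate here is an assumption.

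**The case against.** The strongest reply is that *voided* need not mean dropped from the sum. If one missing item voids the whole score, nothing shifts. Section 9 also promises imputation, and Section 24 has baseline data in hand before dosing. This stands in part: the shifts in the first column of the table are conditional on a reading the plan does not state. But the other readings do not settle the matter. Proration still moves the unchanged patient by 0.6 when one item is lost. Voiding the whole score loses the patient, informatively if testing follows clinical state. The Section 9 sentence names no method and is not reconciled with voiding. Section 24 conflicts with the worst-of-day rule and does not override it.

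A reader might infer that any SOFA item can vanish. The substitutes and scheduled measurements do not support that; the exposure is mainly hepatic and renal, plus GCS in non-intubated patients. A reader might also infer that the AT3 comparison is biased. The documents do not show it: the scheduled assessments are the same in every group, and nothing documents different ward testing by arm.

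Finally, a reaction or bleed after the first infusion is a real change in the patient, so it belongs under contaminated baseline and not under artefact. Nor would such harm be hidden: major bleeding is an endpoint, and Section 12 pauses the study for major bleeding, anaphylaxis or two infusion reactions.

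**Conclusion.** The rule should be changed before analysis. As written, SOFA change has no single definition: the treatment of a voided item is open, it is unreconciled with Section 9, and baseline and follow-up day each have conflicting statements.

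If voided items leave the sum, an unchanged patient can shift by up to 4 points per item, and by 1 to 3 in the assumed example. Between arms, the assumed scenarios give 0 to 0.8 points, and 0 whenever void rates and item scores are equal. The post-infusion baseline problem is real but probably small, on the order of 0.04 to 0.17 points in the arm mean under the assumed reaction rate.

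The Section 7 primary endpoint, the ISTH DIC score, does not depend on this rule. The respiratory sub-score is little affected by voiding but shares the baseline and follow-up-day problems.

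**What to change.** 1. **Replace voiding with an ordered rule.** First, for an item not measured in the scoring period, use the most recent clinical value within a fixed prior window, for example 48 h; for baseline, pre-randomisation values only. Then compute SOFA change only over items available at both time points. In the example this gives 8 − 8, 7 − 7 or 6 − 6, so 0 in each case. Report carried and missing items by arm. Add a sensitivity analysis scoring unmeasured items as 0, so that a new organ failure without a baseline test is not lost. This should stay a sensitivity analysis, because it brings back the shift shown above. State that this rule replaces the Section 9 imputation for SOFA.
2. **Fix the baseline** as the worst values in the 24 h before randomisation (before group assignment for patients with AT3 of at least 100%), replacing admission and excluding any post-infusion Day 1 value.
3. **Choose one follow-up day** and use it in Section 8, Appendix B and Appendix C.

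The cost is a few sentences in Sections 8 and 9 and the appendices, using existing chart values and no new tests. Carried values assume short-term stability. Paired scoring leaves different item sets across patients, and an item the ward never ordered stays missing.

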### Dosing Rationale-

In those COVID(+) patients with an endogenous AT3 activity level <100% and at the discretion of the attending physician, Day 1 infusion of AT3 will be at a dose to be adjusted based on initial body weight up to 100 kg maximum and to a set target plasma activity level of 120% according to the following formula:

$$= \frac{(120\% - \text{baseline AT3}\%)}{1.4} \times \text{body weight (kg)}$$

Based on an example of an 85kg patient with a baseline AT activity level of 90%,

- The dose would be 1,821 units on a dosing schedule of Day 1, 3, 5, 7 & 9
- For a total of approximately 9100 units
- Each Thrombate III vial contains 500 units each reconstituted with 10 mL of Sterile Water for Injection, USP, the final concentration is approximately 50 units per mL.
- Requiring 4 vials per dose or 20 vials per patient

Each 85kg patient will receive ~9100 IU's over 5 doses requiring 20 vials

- (10% overage to account for any dose adjustments needed)
- therefore each patient would require 10,000 IU's
- for a total of 250,000 IU's or 500 vials for the study.

AT3 will be drawn every other day, pre-dose, for monitoring, and verification of 120% target plasma activity level. Dosing schedule will be as follows: Day 1, 3, 5, 7 & 9 a dose will be given if AT3 activity level remains less than 100% on those days, otherwise no dose will be given. Days refer to a 24 hour period.

Data to be collected from the medical record according to the Study Flowsheet (Appendix B) will include:

- a. Demographics: age, comorbidities, medical history, concomitant meds, vital signs, height and weight,
- b. ISTH DIC score and a Sofa Score,
- c. Laboratory values:
  - a. Platelets, PT, INR, PTT, D-Dimer, Fibrinogen, AT3 level, Anti-Xa,
- d. Outcomes:
  - a. Length of Stay, Mortality, change in PF ratio, Vent/ECMO days, # and severity VTE's, # and severity of bleeding events

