**ClinicalTrials.gov Identifier**  
**NCT04899232**

**1) Objectives\***

This will be a prospective, randomized, open label, interventional pilot trial to test the hypothesis that deficient endogenous AT3 is associated with a prothrombotic hyperinflammatory state associated with COVID-19.

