**4) Number of Subjects\***

The study population will be comprised of 75 patients assigned to one of three groups of 25 COVID (+) patients each.

The proportion of subjects with AT3 levels < 100% will be 50/50 randomization of which 25 subjects with AT3 <100% will be standard of care and 25 subjects with AT3<100% will be standard of care with exogenous AT3 supplementation. The third group will be subjects with AT3 levels  $\geq 100\%$ .

- a. 25 patients with endogenous AT3 >100% who receive standard of care only or
- b. 25 patients with endogenous AT3 <100% who receive standard of care only or
- c. 25 patients with endogenous AT3 <100% who receive standard of care plus supplemental AT3.

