**5) Study-Wide Recruitment Methods\***

Potential subjects will be recruited as inpatients under the care of an attending which may include the PI or Sub-Is on this study. Eligibility will be determined by any member of the study team under direction of the PI and in collaboration with the attending physician through review of inclusion and exclusion criteria as compared to the patients’ presentation, diagnoses and medical history. Jackson Health System’s medical records within Cerner will be accessed under a waiver of HIPAA authorization (see section 21). After collaboration with the clinical team and initial screening for entry criteria, a member of the study team will approach potential subjects for consent and enrollment.

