## **24) Drugs or Devices**

### **Drug Administration, Dispensation and Disposition**

Once consent is obtained and necessary baseline data collected, and if the subject is enrolled and falls into the Thrombate III infusion arm, they will begin receiving THROMBATE III (Antithrombin III [Human]) at 120% target dose every other day for 9 days.

Study drug will be packaged, labeled, and delivered to the clinical center by the drug manufacturer. All medication supplied to be used in this study will be manufactured, tested, labeled, and released according to current legal requirements and Good Manufacturing Practice (GMP).

The pharmacy will conduct an inventory upon receipt of the clinical supplies and will acknowledge receipt of the supplies to the sponsor. A copy of the shipping documents will be maintained for records. Study drug will be stored in accordance with the package insert in a secure location until dispensed to the subject.

Study drug kits will be dispensed according to the dosing schedule. The pharmacy will keep a current record of the inventory and dispensing of all clinical supplies. This record will be made available to the sponsor's monitor for the purpose of accounting for all clinical supplies. Any discrepancy or deficiency will be recorded, with an explanation. All supplies sent to the investigator will be accounted for and in no case will clinical supplies be used in an unauthorized situation.

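### The Dosing Rationale makes the Day 1 AT3 infusion subject to undefined attending discretion, while the rest of the protocol makes infusion follow random assignment

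*Combined protocol and SAP*

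**What the plan says.** The trial is described in section 1 as a "prospective, randomized, open label, interventional pilot trial". Section 4 sets a 1:1 split among patients with AT3 below 100% ("The proportion of subjects with AT3 levels < 100% will be 50/50 randomization"). One arm is "25 patients with endogenous AT3 <100% who receive standard of care only or" and the other is "25 patients with endogenous AT3 <100% who receive standard of care plus supplemental AT3".

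The places that state a condition for infusion are these:

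- **Section 8, Procedures Involved:** the 50 patients with AT3 below 100% "will be will be randomly assigned to begin" either standard of care plus AT3 or standard of care only.
- **Section 8, Dosing Rationale, opening sentence:** for patients with AT3 below 100% "and at the discretion of the attending physician, Day 1 infusion of AT3 will be at a dose to be adjusted". The assigned arm is not mentioned.
- **Section 8, Dosing Rationale, schedule:** doses on Days 1, 3, 5, 7 and 9 depend only on AT3 still being below 100% that day. Discretion is not mentioned.
- **Section 24, Drugs or Devices:** an enrolled patient who "falls into the Thrombate III infusion arm, they will begin receiving THROMBATE III". Discretion is not mentioned.
- **Appendix B, footnote 1:** dosing applies only to patients randomised to AT3 infusion whose AT3 meets the level criterion. Discretion is not mentioned.

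Section 5 adds that patients are recruited "under the care of an attending which may include the PI or Sub-Is on this study".

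**The concern.** The two groups with AT3 below 100% form the only randomised contrast in the trial. Its value depends on assignment, and not a later judgement about the patient, deciding who is offered AT3. The opening sentence of the Dosing Rationale adds a second, undefined condition. It gives no grounds and no time point, and it does not ask for a reason to be recorded.

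If the judgement is made with the arm known, it can act in only one arm, because no infusion is planned in the other. The attending may be an investigator, and the decision may track prognosis, with sicker or less sick patients left uninfused. Two consequences follow. A comparison as randomised stays valid as a comparison of assignments but is pulled towards no difference. A comparison by treatment received loses the protection of randomisation. Section 9 defines no analysis set, so the plan does not say which would be used. Reasons not recorded during the trial cannot be recovered afterwards.

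**Working it through.** **1. Is there a contradiction in the current text?** Set side by side, the conditions for a Day 1 infusion are:

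| Place | AT3 below 100% | Assigned to AT3 | Attending discretion |
|---|---|---|---|
| Section 4 | yes | yes | no |
| Section 8, Procedures | yes | yes | no |
| Section 8, Dosing Rationale, opening | yes | not mentioned | yes |
| Section 8, Dosing Rationale, schedule | yes | not mentioned | no |
| Section 24 | not mentioned | yes | no |
| Appendix B, footnote 1 | specified level | yes | no |

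The opening sentence of the Dosing Rationale is the only place with a discretion condition. It differs from the other sections and from the schedule under the same heading.

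**2. The plan's own figures.** The documents give no power, effect size or SD for the 75 patients, so there is no power statement to test. The figures attached to this text are the worked dose and the drug supply, and they reproduce:

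- Dose: (120 − 90) / 1.4 × 85 = 1,821 units.
- Five doses: 5 × 1,821.4 = 9,107 units (stated as about 9,100).
- Vials: 1,821 / 500 rounds up to 4 per dose; 5 × 4 = 20 per patient.
- With 10% overage: 9,100 × 1.1 = 10,010 IU (stated as 10,000).
- Study total: 25 × 10,000 = 250,000 IU; 250,000 / 500 = 500 vials.

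The supply is sized for 25 infused patients, the whole AT3 arm. It allows neither for discretionary non-infusion nor for infusing controls.

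**3. Illustration of dilution.** Inputs: 25 per arm (section 4) and significance level 0.05 (section 9). Assumptions: a two-sided test, a two-sample t test on a continuous outcome, a share f of the AT3 arm never infused, and no effect in those patients.

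- With everyone treated as assigned, 25 per arm has 80% power for a standardised difference d = 0.81. The normal approximation gives (1.96 + 0.84) × √(2/25) = 0.79.
- With share f not infused, the expected difference as randomised is d × (1 − f). The effect in treated patients needed for 80% power is d / (1 − f).

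| f (assumed) | Expected difference (SD) | Power | Effect in the treated for 80% power (SD) |
|---|---|---|---|
| 0% | 0.81 | 80% | 0.81 |
| 10% | 0.73 | 71% | 0.90 |
| 20% | 0.65 | 61% | 1.01 |
| 30% | 0.57 | 50% | 1.16 |

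The normal approximation, starting from 0.79, gives the same powers to the nearest percent.

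**The case against.** **Timing.** A reader might infer that the discretion operates after randomisation. The text does not say so. The sentence could describe a suitability check before assignment or, since its main clause concerns how the dose is set, discretion over the dose. Section 5 already has eligibility determined with the attending, and exclusion criterion n in section 3 already allows study-team judgement. This stands: timing is an open question. In favour of the later reading, the words attach to the Day 1 infusion, a step that sections 8 and 24 and Appendix B place after assignment, and pre-enrolment judgement is already covered elsewhere. The text should settle it.

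**Control arm.** Because the sentence speaks of all patients with AT3 below 100%, a reader might infer that controls could be infused. The documents do not support this. Sections 4 and 8 give that arm standard of care only, Appendix B limits dosing to those randomised to AT3, and the supply covers 25 patients. No contamination is claimed.

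**Day 1 only.** The discretion is tied to Day 1. Under the schedule rule, a patient not infused on Day 1 would still be dosed on Day 3 if AT3 is below 100%. This stands: the never-infused calculation overstates the loss if later doses are given.

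**Size and relevance.** The non-infusion rates have no source in the documents, and a pilot with no stated power has none to lose. Section 9 compares fastest with slowest recovery and names no test between arms, so dilution matters only if the randomised arms are compared. Both points stand, and they keep the numbers illustrative. They do not remove the need to keep and record treatment as assigned, because a later analysis cannot repair unrecorded selection.

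**Existing records.** Section 24 requires pharmacy dispensing records, and section 10 records drug interruption or discontinuation against adverse events. These show whether drug was given and capture actions linked to adverse events. They do not capture a decision not to infuse for other reasons. Withdrawal and discontinuation for safety (sections 11 and 13) will cause some non-dosing whatever is done here.

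**Conclusion.** The inconsistency is real and in the current text: one sentence makes the Day 1 infusion subject to undefined discretion without naming the arm, and the other sections make infusion follow assignment. The documents do not say when the discretion applies, nor how patients assigned but not infused are analysed.

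The bias is conditional. It arises if the discretion is exercised with the arm known, and the open-label design and the attending's possible investigator role make that possible. It would then act as selective non-infusion in the AT3 arm, diluting an as-randomised contrast and biasing an as-treated one. The size is unknown. The fall from 80% to about 71%, 61% or 50% rests on assumed rates of 10%, 20% and 30% never infused, no effect in those patients, a two-sided t test, and a comparison between arms that section 9 does not yet name.

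This is worth correcting because it is cheap, not because a large loss has been shown. No view is taken on which clinical rule is right.

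**What to change.** 1. Reconcile the opening sentence of the Dosing Rationale with its own schedule rule, with sections 4, 8 and 24, and with Appendix B footnote 1, so that one statement says who is infused, on what condition and when that is decided.
2. If a judgement on suitability for infusion is kept, record it before assignment so that it acts equally on both randomised arms.
3. Add a field to the case report form for the reason for any later non-infusion.
4. State in section 9 that the two arms with AT3 below 100% are compared as randomised, including patients assigned to AT3 but not infused.

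The cost is protocol wording, one screening entry and one reason field. The downside is that a few patients may be excluded before randomisation. The clinical grounds for giving or withholding AT3 remain for the investigator to define.

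### The protocol does not say which AT3 value sets the dose on Days 3, 5, 7 and 9, and its five-dose example meets the 120% target only if AT3 is back at baseline

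*Combined protocol and SAP*

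**What the plan says.** All the dose amounts are in Section 8, Dosing Rationale.

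- The formula is introduced for the first infusion: "Day 1 infusion of AT3 will be at a dose to be adjusted based on initial body weight up to 100 kg maximum". The same sentence fixes the aim of that dose, which is "to a set target plasma activity level of 120% according to the following formula". The AT3 value in the formula is the baseline one, and the divisor is 1.4.
- The worked example is an 85 kg patient with baseline AT3 of 90%. It states: "The dose would be 1,821 units on a dosing schedule of Day 1, 3, 5, 7 & 9". The total is then given: "Each 85kg patient will receive ~9100 IU's over 5 doses requiring 20 vials".
- The supply estimate follows, with a "10% overage to account for any dose adjustments needed", leading to 10,000 IU per patient and 250,000 IU or 500 vials for the study.
- AT3 is measured before each alternate-day dose, for monitoring and to verify the 120% target. On Days 1, 3, 5, 7 and 9, "a dose will be given if AT3 activity level remains less than 100% on those days, otherwise no dose will be given".

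Two other places mention later dosing. Section 24 (Drug Administration, Dispensation and Disposition) describes the infusion arm's alternate-day doses only by the 120% target, with no formula. Footnote 1 to the Appendix B flowsheet says only that dosing depends on AT3 being at a specified level.

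**The concern.** The text makes the pre-dose AT3 decide whether a later dose is given. It never says whether that value also decides how much. Two readings are open: repeat the baseline-derived amount, as the example does, or re-enter that day's AT3 in the formula, as a 120% target at each dose would suggest. They give the same amount only when AT3 has returned to its baseline value.

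This affects up to four of the five doses in the only active arm (25 patients, Section 4). If staff read the text differently, exposure in that arm will vary for reasons unrelated to the patients, and all the scheduled doses fall within the Day 9 window of the primary endpoint (Section 7). It also bears on safety. The Drug Interactions text in Section 13 says that AT3 enhances the effect of heparin, Section 12 pauses the study for any major bleeding event, and major bleeding events are a secondary endpoint.

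**Working it through.** **Inputs from Section 8:** target 120%; divisor 1.4; weight capped at 100 kg; example patient 85 kg with baseline AT3 of 90%; re-dosing only below 100%. **Assumptions:** every pre-dose level on Days 3 to 9, and every baseline other than 90%. The documents give no distribution for either.

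**1. Reproduce the plan's figures.** Dose = (120 − AT3) / 1.4 × weight.

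- One dose: (120 − 90) / 1.4 × 85 = 1,821.4 units; the plan says 1,821.
- Five doses: 5 × 1,821.4 = 9,107 units; the plan says about 9,100.
- With overage: 9,100 × 1.1 = 10,010; the plan says 10,000.
- Study supply: 25 × 10,000 = 250,000 IU, and 250,000 / 500 = 500 vials, as stated.

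All agree. The total shows that the example is five equal baseline-derived doses.

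**2. Predicted level after a later dose.** The formula implies a rise of 1.4 × dose / weight percentage points. Up to 100 kg, a repeated baseline dose raises AT3 by (120 − baseline), so

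predicted level = pre-dose AT3 + (120 − baseline AT3) = 120 + (pre-dose AT3 − baseline AT3).

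This equals 120% only if the pre-dose level equals baseline. It is higher if AT3 has risen and lower if AT3 has fallen. Because no dose is given at 100% or above, the excess is always less than (100 − baseline) points.

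**3. The two readings for an 85 kg patient.**

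| Baseline AT3 | Pre-dose AT3 | Repeated baseline dose (units) | Formula on that day's AT3 (units) | Predicted level with repeated dose |
|---|---|---|---|---|
| 90% (plan's example) | 80% | 1,821 | 2,429 | 110% |
| 90% | 90% | 1,821 | 1,821 | 120% |
| 90% | 95% | 1,821 | 1,518 | 125% |
| 90% | 99% | 1,821 | 1,275 | 129% |
| 60% (assumed) | 95% | 3,643 | 1,518 | 155% |

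For instance, at 95% the second reading is (120 − 95) / 1.4 × 85 = 1,518 units. In the plan's own example the excess over target is under 10 points, and the repeated dose at 99% is 1,821 / 1,275 = 1.43 times the recalculated one. With the assumed 60% baseline, the ratio is 3,643 / 1,518 = 2.4.

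**4. When a ratio above two needs lower baselines.** The ratio of the repeated to the recalculated dose is (120 − baseline) / (120 − pre-dose). It exceeds 2 only if baseline is below 78% with a pre-dose level of 99%, or below 70% with a pre-dose level of 95%. Sections 4 and 8 require AT3 below 100% for randomization and state no lower limit, so such baselines can be enrolled. How often they would occur is unknown.

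**5. Above 100 kg.** The cap reduces the rise to (120 − baseline) × 100 / weight. For 120 kg and an assumed baseline of 70%, the rise is 50 × 100 / 120 = 41.7 points, so a repeated dose exceeds 120% only if the pre-dose level is above 120 − 41.7 = 78.3%.

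**6. Effect on the supply figure.** If that day's AT3 is used, the example's five-dose total holds only if the five pre-dose levels average 90%. With 90% on Day 1 and 95% on the other four days it is 1,821.4 + 4 × 1,517.9 = 7,893 units. With 80% on those four days it is 1,821.4 + 4 × 2,428.6 = 11,536 units, above the 10,000 allowed per patient.

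**The case against.** The strongest reply is that the example is a supply estimate. Its bullets run straight into vials per dose, per patient and for the study, and its totals are approximate. A constant level of 90% is a reasonable simplification for ordering drug. The overage line expects doses to change, and Section 24 describes each dose by its target and not by a fixed number of units. Read together, these lean towards recalculating each dose. This stands as far as it goes: repetition is one reading and not an explicit order. But the example is also the only text giving an amount for Days 3 to 9, the overage line gives no rule for adjustment, and Section 24 names no AT3 value. The reference to the attending physician's discretion sits in the Day 1 sentence and does not settle the matter either.

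A second reply is that Section 13 already provides regular coagulation tests, adjustment of the anticoagulant and monitoring for bleeding. These bear on the risk, but they do not say how much AT3 to give.

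Stronger readings are tempting and not supported. A reader might infer that the example is miscalculated; every figure reproduces. A reader might infer that repetition overshoots whenever AT3 has risen; no dose is given at 100% or above, the weight cap can absorb a small rise, and a fall in AT3 gives an undershoot. A reader might infer that twofold differences are typical, or that levels above 120% are shown to be harmful. The first needs assumed baselines well below the plan's example, and the documents set no upper AT3 limit from which to argue the second.

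**Conclusion.** The point holds as an internal inconsistency with a missing rule. Section 8 ties the formula to Day 1 and baseline AT3, carries the resulting amount unchanged to Day 9 in its example, and sets a 120% target that the repeated amount meets only if AT3 is back at baseline. Nothing elsewhere resolves it.

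In the plan's own example the predicted level runs from 110% to 129% for pre-dose levels of 80% to 99%, and the two readings differ by up to 1.43-fold when AT3 has risen. Larger gaps, such as 2.4-fold at a baseline of 60% and a pre-dose level of 95%, are admissible under the entry rules but rest on assumed levels. All predicted levels use the protocol's own 1.4 factor and are not forecasts of what patients would show. The point should be settled before dosing because it concerns the amount of study drug in the only active arm.

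**What to change.** The sponsor and investigator should reconcile five items: the Day 1 formula, the five-dose example and its total, the 120% target, the below-100% condition for re-dosing, and the description in Section 24. The amended text should state which AT3 value enters the formula on Days 3, 5, 7 and 9. The example and the 9,100-unit and 500-vial figures should then follow from that statement, or be labelled as a supply estimate only. Which rule applies is for them to decide; none is proposed here.

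The cost is a short protocol clarification and a matching edit to Section 24. No extra test is needed, because AT3 is already measured before each dose. The drug supply estimate may need to be recalculated.
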